Parents who decline participation or whose children are ineligible for the trial will be invited to take part in an observational study. In all cases trial participation will be invited prior to extending any invitation to take part in the OCS. This is in order to prioritise entry into the RCT. Participation in the RCT would not involve any change in their management, but would involve collecting data about their presentation, management and follow-up. If parents decline participation in the observational study then they will not be entered into the study but we will record anonymous data in a screening log.

Entry into the RCT or OCS

Entry into the RCT or OCS will be signified by the completion of a valid consent form. Parents agreeing to take part in the RCT will be asked to sign a consent form after which the Responsible Clinician will sign the Trial Prescription

and the parent will be given the Patient Pack and, if the child is allocated to one of the two treatment arms of the RCT, the trial medicines. For parents or carers agreeing to take part in the OCS, the parent will be asked to sign a consent form, either while with the Responsible Clinician, or soon after the consultation and before leaving the site. Any patient subsequently found ineligible or declining to participate will be recorded on a screening form with brief reasons for ineligibility or declining, the remaining data destroyed and a protocol deviation recorded.

Online data collection means instant notification of recruitment to the lead Centre (Bristol). For all patients, including patients recruited using paper forms, GP sites will be asked to fax to the Bristol trial centre by the end of the same working day, evidence of valid consent and the parent's contact details. This will trigger a telephone call to the parent (usually on the same or following day) from the CEDAR trial nurse to address any questions or concerns about the trial or trial medicines.

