- (b) a suitably qualified and GCP-trained Nurse or other healthcare professional, who has been trained in the trial procedures, and with oversight from a GCP-trained GP or other medically qualified doctor (oversight in this instance is confirmation that the eligibility decision is correct, established by means of the GCP-trained doctor's signature on the trial prescription prior to the issue of the trial medication), OR
- (c) A suitably qualified and GCP-trained Advanced Nurse Prescriber/Practitioner who has been trained in the trial procedures, with oversight from a GCP-trained GP or other medically qualified doctor (oversight in this instance is confirmation that the eligibility decision is correct, established by means of the GCP-trained doctor's signature on the trial prescription within a reasonable time scale following recruitment, as above).

(ii) Consent

Informed consent (which may or may not be accompanied by child assent, depending on the age and understanding of the child and at the discretion of the clinician and parent) will be obtained for all children by:

- (d) a GCP-trained GP or Nurse who has been trained in the trial procedures, OR;
- (e) a non GCP-trained healthcare professional (GP or Nurse) who has been trained in the trial procedures by a GCP-trained GP, and with oversight from a GCP-trained GP (oversight in this instance is: (1) written confirmation from a GCP-trained GP that the member of staff is sufficiently qualified and experienced to take consent, on behalf of the recruiting site, for this trial; and (2) countersignature on the consent form by the GCP-trained GP prior to the issue of the trial medication).

(iii) Issue of the trial medication

The trial medication may be issued to the parents of participating children, who have been recruited to one of the two ear drop arms, by a suitably qualified and GCP-trained GP, Nurse or other healthcare professional who has received training in the trial procedures.

Persons authorised to undertake the above activities on behalf of the recruiting site, will be documented on the trial delegation log.

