9.6. Randomisation and administration of patient packs

The trial medication may be issued to the parents of participating children, who have been recruited to one of the two ear drop arms, by a suitably qualified and GCP-trained GP, Nurse or other healthcare professional who has received training in the trial procedures.

Trial medicines will be administered in a manner designed to prevent loss of concealment pre-randomisation (see sections 7.2 and 12.3). Once the child has been confirmed to be eligible for the trial, and once written, informed consent has been obtained from the parent, the clinician will select the next sequentially numbered Patient Pack and open this in the presence of the parent. The presence of a Medicine Pack within the Patient Pack, vs the presence of a non-medicinal item (of equivalent weight) will indicate to the clinician whether the child has been allocated to one of the treatment (active ear drops or placebo ear drops) arms, or to the control (no ear drops) arm.

The transition from the initial 2 arm pilot, to the 3 arm full trial once the placebo is available, will be managed in order to reduce wastage of Patient Packs. From the point at which the placebo is available, participating sites will be transferred from the 2 arm pilot into the 3 arm trial once they have used up their allocation of 2 arm Patient Packs. Any new site joining the trial after the point of placebo availability will be set up to run the 3 arm trial.

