12.5. Statistical analysis

Quantitative analysis

The analysis and presentation of the trial will be in accordance with the CONSORT guidelines and a full analysis plan developed. Descriptive statistics will be used to assess balance in the randomised arms at baseline and will be presented as means and standard deviations for normally distributed variables, medians and inter-quartile ranges for any skewed variables, or numbers and percentages.

The first part of the primary comparison will be the prevalence of antibiotic use at Day 8 post consultation (where Day 1 is the day of randomisation) between those children receiving active eardrops and those receiving no drops (usual care) and will be analysed on an intention to treat basis. The time between consultation and antibiotic consumption will also be explored. Logistic regression will be utilised and the findings adjusted for marked imbalance at baseline (e.g. that differ by more than 0.5 standard deviations for age or univariable significant differences in proportions such as those with bilateral AOM). Post randomisation health care related variables such as other analgesics taken by the child (we will record the timing of the last dose of oral analgesics given to the child that day, prior to the daily parent-rated child ear pain score) will not be adjusted for in the main model but will be mediated for in a secondary analysis. For any continuous outcomes that are clearly non-normally distributed, appropriate transformations will be documented and justified in the model. To assess the potential effects of missing data, multiple imputation methods will be utilised in a sensitivity analysis.

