13.2. Data management

Data collection, management and archiving will be conducted in accordance with the principles of the Data Protection Act and Good Clinical Practice guidelines. We will use a secure, web-based (RedCap [Harris et al 2009]) data collection platform which will be developed, validated, hosted and supported by the University of Bristol. The system will provide a secure login to allow collaborator authentication and direct data entry, with a full audit trail. The system will also maximise access (from any primary care sites across England and Wales) while minimising risk of data loss, duplication and security lapses from laptops and other portable media. The system will incorporate data entry and validation rules to reduce data entry errors, and management functions to facilitate auditing and data quality assurance. A bespoke web-based system will be developed to maximise the user-friendliness of data entry for clinicians and for parents.

All patients will be consented using paper consent forms, pre-numbered with the Patient ID number, and provided in the Patient Pack. Consent forms will be scanned and linked to the patient's medical record by site staff and sent by secure fax to the Bristol Centre on the day of recruitment, as well as being returned to the Bristol Centre by pre-paid return addressed envelopes.

While on-line data entry will be the default method of data capture, paper-based alternatives will be provided to accommodate clinician preference and allow recruitment to continue in the unusual event of website inaccessibility. Responsible Clinicians will be asked to enter all data onto the website by the end of day zero, except participant registration details, which will be entered by Bristol Centre staff onto an off-line trial management database. Once data are added to the web-based database, all patient paperwork (except consent forms and registration details) will be stored at the primary care site until completion of participant recruitment. Patient identifiers will be kept on a separate system from the clinical data and data protection requirements will be further enforced by best practice trial management procedures. Paper versions saved on site will be archived by the University of Bristol at the end of the trial according to local policy for paediatric clinical trials, with all data retained for at least 15 years post trial closure in line with University of Bristol procedures.

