APPENDIX 10: Participant Withdrawal

Parents have the right to withdraw their children, and children have a right to withdraw themselves, from the trial at any time for any reason, without their medical care being affected. Parents and children also have the right to decline to continue with any aspect of the research, without withdrawing and without their medical care being affected.

Data already collected will continue to be used in the trial and parents who withdraw their children from the trial will be asked if they are still willing to provide follow-up data via the Symptom and Recovery Questionnaire. Furthermore, we intend to conduct telephone interviews with parents who decide to withdraw (n=10). If a child is withdrawn, the reason for and type of withdrawal will be documented in the CRF. For example, type of withdrawal may include:

- 1. Trial use of baseline (CRF) data
- 2. Use of trial medication
- 3. Completing Symptom and Recovery Questionnaire
- 4. Receiving telephone calls, letters, email or texts to support Symptom and Recovery Questionnaire completion
- 5. Review of their primary care record
- 6. Completion of the postal Quality of Life (QoL) questionnaire at 3 months
- 7. Any combination or all of the above

The Principal Investigators also have the right to withdraw children from the trial drug in the event of inter-current illness, Adverse Events (AEs), Serious Adverse Events (SAEs), Suspected Unexpected Serious Adverse Reactions (SUSARs), protocol violations, administrative reasons or other reasons. The reason for withdrawal will be documented in the CRF. If the child is withdrawn due to an adverse event, the investigator will arrange for follow-up visits or telephone calls until the adverse event has resolved or stabilised. It is understood by all concerned that an excessive rate of withdrawals can render the trial un-interpretable, therefore unnecessary withdrawal of children will be avoided.

We will request return of the trial Medicine Packs from the parents of children who are withdrawn from the trial. Recruitment will continue until the required number of follow-up datasets are received, thereby replacing any children who have been withdrawn before Symptom and Recovery Questionnaire outcomes are collected.

A formal SOP will be developed to describe the process for declining to continue with elements of the research and for withdrawing from the trial.

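### The protocol contradicts itself on destroying data after entry and on where the consent form is packed; one reading of each could bias the open primary comparison

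*Protocol*

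**What the plan says.** **Data after entry.** Section 6.4 of the protocol (Entry into the RCT or OCS) fixes the point of entry: "Entry into the RCT or OCS will be signified by the completion of a valid consent form". It then has the trial prescription signed and the Patient Pack given out, with trial medicine where allocated. Next it says: "Any patient subsequently found ineligible or declining to participate will be recorded on a screening form", with brief reasons, "the remaining data destroyed and a protocol deviation recorded".

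Section 12.5 says that the primary comparison "will be analysed on an intention to treat basis", and 7.6 says the same of the primary analyses. Appendix 10, on children who withdraw, says: "Data already collected will continue to be used in the trial". It also asks withdrawing parents whether they will still give follow-up data.

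On eligibility checks, 6.11(i)(b) requires a doctor's confirming signature before medication is issued when another nurse or healthcare professional assesses the child. For advanced nurse prescribers or practitioners, 6.11(i)(c) accepts the doctor's "signature on the trial prescription within a reasonable time scale following recruitment, as above".

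**Consent form and pack.** Section 13.2 says: "All patients will be consented using paper consent forms, pre-numbered with the Patient ID number, and provided in the Patient Pack". Section 7.2 puts the medicine pack, or a dummy item of equal weight, in the same pack so that the clinician stays unaware of allocation until randomisation. Section 9.6 says that once the child is confirmed eligible and written consent is in hand, "the clinician will select the next sequentially numbered Patient Pack and open this in the presence of the parent". Section 12.3 and Appendix 9 give the same order. Section 9.2 has the trial number written on the consent form once the child has entered, not printed beforehand.

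**The concern.** The primary comparison, active drops against no drops, is open. It is protected by two things only: allocation stays unknown until the family is committed, and everyone randomised is counted afterwards. Each of these is contradicted somewhere in the protocol.

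If the 6.4 rule is applied to randomised children, they leave the analysis and their data cannot be recovered by any later analysis plan. If the consent form is reached by opening the pack, a parent hoping for drops can see that there are none and decline to sign. Under 6.4 that child has never entered, so the refusals could thin out the no-drops arm selectively and leave only a screening record.

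Continuing recruitment to make up lost datasets, as Appendix 10 provides for withdrawn children, would restore numbers but not comparability.

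**Working it through.** **1. Does the 6.4 rule reach randomised children?** The wording does not exclude them.
- The rule follows consent and pack hand-over, and the word *subsequently* has no end point.
- Earlier in 6.4, children who are ineligible or whose parents decline before entry are dealt with separately: they are offered the observational study or, failing that, recorded anonymously in a screening log.
- Recording a protocol deviation fits a child who has already entered better than an ordinary screening failure.

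The clearest exposure is a randomised child later found ineligible. Appendix 10 deals with withdrawal, so 6.4 is the only specific data rule for that child. The route exists because under 6.11(i)(c) the signature confirming that the eligibility decision was correct may follow recruitment.

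**2. Can 13.2 and 9.6 both be followed?** Not if the form is inside the sealed pack. The parent must sign before the pack is opened, but the form would be reachable only by opening it.
- Three-arm phase: opening shows drops or no drops, which is the primary comparison. Active versus placebo stays masked.
- Two-arm pilot: opening shows the full allocation, since the only drops are active.

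**3. Size.** No removal rate is given, so the protocol has no figure of its own to reproduce on this point. Its sample sizes are used below and were checked first. With two-sided alpha 0.05, 90% power and continuity correction, 80% v 60% gives 119 per arm and 90% v 70% gives 92, as stated in 12.1. The pain calculation gives 132 against 133 stated. With 20% attrition, 119/0.8 = 148.75, so 149; 133/0.8 = 166.25, so 167; and 3 × 167 = 501.

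*Bias, as an illustration.* Let p be the true consumption in the no-drops arm (80%, the lower end of the range in 12.1), d the share of that arm removed, and q the share of removed children who would have used antibiotics. The values of d and q are assumptions.

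Observed rate = (p − d·q)/(1 − d)

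| d | q | Observed rate | Shift (points) |
|---|---|---|---|
| 5% | 100% | (0.80 − 0.05)/0.95 = 78.9% | −1.1 |
| 5% | 80% | (0.80 − 0.04)/0.95 = 80.0% | 0 |
| 5% | 50% | (0.80 − 0.025)/0.95 = 81.6% | +1.6 |
| 10% | 100% | (0.80 − 0.10)/0.90 = 77.8% | −2.2 |
| 10% | 80% | (0.80 − 0.08)/0.90 = 80.0% | 0 |
| 10% | 50% | (0.80 − 0.05)/0.90 = 83.3% | +3.3 |

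These shifts compare with a planned difference of 20 points.

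*Power, as an illustration.* Children analysed per arm = 167 × (1 − d) × 0.8, with removal now assumed in every arm.

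| d | Analysed per arm | Power, 80% v 60% | Power, pain (1.0, SD 2.5) |
|---|---|---|---|
| 0% | 133.6 | 95.0% | 90.5% |
| 5% | 126.9 | 94.0% | 89.0% |
| 10% | 120.2 | 92.8% | 87.3% |

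Power stays near or above target. The risk is bias from selective removal, not loss of size.

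**The case against.** The best defence is that the operative sections run the right way. Consent comes before the pack in 6.4, 9.6, 12.3 and Appendix 9. Neither the contents list in 7.2 nor the glossary entry for the pack names a consent form. Section 9.2 adds the number after entry, and the glossary assigns the Patient ID after written consent. The sentence in 13.2 is a single data-management statement covering all patients, including observational-study children whose packs hold no medicine. On the data side, the protocol distinguishes declining from withdrawing. A parent who signs, sees no drops and leaves can be read as a withdrawal under Appendix 10, whose data are kept.

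Much of this stands, and it rules out several stronger inferences that a reader might draw:
- *That intention to treat and concealment both fail outright.* Each fails only if the contradicting sentence is the one followed.
- *That allocation is visible before consent for every child.* This requires sites to follow 13.2 over the procedural sections, with the form inside the sealed part.
- *That data destruction is bound to occur.* Section 6.11(i)(c) makes late ineligibility possible, but no rate of overturned decisions is given, and 6.11 offers nurse practitioners an advice route for borderline cases.
- *That children later found to have G6PD deficiency would be erased.* Only known deficiency or known family history excludes, so a first diagnosis after entry is not ineligibility.
- *That safety records would be lost.* Sections 8.1 and 8.2 require adverse events to be recorded, and 6.4 does not say that it overrides them.

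What the defence does not remove: 6.4 has no limit to unrandomised children, Appendix 10 does not cover later-found ineligibility, and the pack contents in 7.2 and the glossary leave room for a consent form.

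**Conclusion.** The point holds as two internal contradictions. Section 6.4 conflicts with the intention-to-treat statements in 7.6 and 12.5 and sits badly with Appendix 10; the main gap is the randomised child later found ineligible. Section 13.2 conflicts with 9.2, 9.6, 12.3 and Appendix 9 if the form is inside the sealed pack.

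The amount of bias cannot be stated. Under the assumptions shown (80% consumption, 10% removed from the no-drops arm only), it lies between −2.2 and +3.3 points as q runs from 100% to 50%, and is zero if the removed children resemble the rest of their arm. So neither a particular direction nor a large bias can be claimed. The passages should still be reconciled, because destroyed data and lost concealment cannot be repaired at the analysis stage.

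**What to change.** **Section 6.4.** Confine data destruction to children who were never randomised. State that every randomised child stays in the intention-to-treat set, with data kept and follow-up continued, subject only to withdrawal of consent to data use. Ineligibility found later is logged as a deviation.

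**Section 13.2 and the glossary entry for the Patient Pack.** Supply consent forms outside the sealed pack and add the Participant ID after consent, in line with 9.2, 9.6 and 12.3.

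The cost is a few sentences and a change in where one form is packed, with no extra participants.

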6.5. Factors influencing recruitment, and how these factors will be monitored

The following six recruitment assumptions are presented for two reasons: (i) to illustrate our understanding of the challenges associated with recruiting to this trial; and (ii) to focus our recruitment strategy such that we collect detailed information to test each of the assumptions. Importantly, should recruitment be slower than expected, the collection of these data will allow us to establish which of the six recruitment steps are the problems requiring resolution, which will be achieved using our multidisciplinary team, including PPI.

- a) Age and season related incidence of acute otitis media (AOM) to GP practices has been estimated from the Royal College of General Practitioners (RCGP) 2011 report for AOM in children.² Importantly, these estimates are post introduction, in 2006 and 2010 respectively, of the pneumococcal 6 and 13 valent vaccines (which resulted in a fall in AOM incidence) and allow adjustments for seasonal variation. We have calculated the probability of AOM presentation to general practices per quarter for a child aged 12 months to 10 years (CEDAR age criteria) to be between 0.062 (summer trough) and 0.153 (winter peak).
- b) GP practice incidence has been calculated assuming an average (mean) list size of by 65003 and the proportion of children between 12 months and 10 years as 0.12 (Office of National Statistics report 0.17 of the population was aged less than 14 years in 2011).4 Therefore, we estimate an average GP practice will have between 48 (summer trough) and 119 (winter peak) children aged12 months to 10 years present with AOM per quarter.
- c) Proportion of presenting children invited to participate we have assumed will be 0.2, since many children will present to primary care sites at inconvenient times (e.g. insufficient recruiting staff capacity). This proportion will be monitored by asking sites to use standard diagnostic Read codes (e.g. otalgia and acute otitis media) allowing the study team to estimate presentation rates.
- d) Proportion meeting eligibility criteria we have assumed to be 0.66, since the most prevalent CEDAR exclusion criterion (bilateral AOM) was present in 34% of all children in a 2006 systematic review.⁵ This is a conservative estimate since the CEDAR exclusion criterion is bilateral AOM in children under 2 years (these data not given). This proportion will be monitored through clinician completed screening logs.
- e) Proportion of invited children agreeing to participate we have conservatively assumed to be 0.25, though our PPI groups suggests this may be higher, with up to 0.66 indicating they would wish to participate. This proportion will be monitored through clinician completed screening logs.
- f) The proportion of children with primary outcome data we have conservatively assumed to be 0.8 (previous similar trials^{6 7} have achieved proportions in excess of 0.9). This proportion will be monitored using symptom diaries.

